4.2 Efficacy endpoints

For further details on efficacy endpoints, see Section 14 (Appendix II) of the protocol. For the evaluation of tumor-response related endpoints, response is assessed by investigator and BIRC according to RECIST 1.1.

Response and progression evaluation will be performed according to the Novartis RECIST 1.1 guidelines, included in Section 14 (Appendix II) of the LDK378A2109 protocol.

The text below gives more detailed instructions and rules needed for programming of the analyses described in [Sections 3.2.10](#)

4.2.1 Implementation of RECIST guidelines

Disease progression

PD should only be assigned if it is confirmed by an objective assessment method as per RECIST 1.1 (e.g. radiologic scan, histology for bronchoscopy, photos for skin lesions). If a new lesion is detected using an objective assessment method other than radiologic scan, it should be entered on the 'New lesion' RECIST eCRF with appropriate method (or method='Other').

In particular, discontinuation due to disease progression or death due to progressive disease, without supporting objective evidence (as defined above), will not be considered as PD in the determination of best overall response, the derivation of any efficacy endpoint or efficacy analysis.

Change in imaging modality

Per RECIST 1.1, a change in methodology can be defined as either a change in contrast use (e.g. keeping the same technique, like CT, but switching from with to without contrast use or vice-versa, regardless of the justification for the change) or a change in technique (e.g. from CT to MRI, or vice-versa), or a change in any other imaging modality. A change in methodology will result by default in a UNK (unknown) overall lesion response assessment. A change from conventional to spiral CT and vice versa while keeping same contrast use (e.g. switching from spiral CT with contrast to CT with contrast) is not considered a change in imaging modality. However, a response assessment other than the Novartis calculated UNK response may be

accepted from the investigator or BIRC if a definitive response assessment can be justified based on the available information. Potential discrepancies between the modality used and overall lesion response reported by the investigator (e.g. change in modality but investigator assessment of response is different from UNK) will be queried during the data validation process.

Determination of missing adequate tumor assessments

For the computation of ORR, patients without any radiological assessment after the start date of study drug will be counted as failure.

Partial or complete responses reported prior to any additional anticancer therapy will be considered for ORR computation irrespective of the number of missed assessments before response. In this section, the ‘missing adequate assessment’ is defined as assessment not done or assessment with overall lesion response equal to UNK. For the sake of simplicity, the ‘missing adequate assessment’ will also be referred as ‘missing assessment’.

As detailed in Section 14 (Appendix II) of the LDK378A2109 protocol, the PFS censoring and event date options depend on the presence and the number of missing tumor assessments. *For example, an event occurring after two or more missing assessments is censored in the analysis of PFS at the last adequate tumor assessment before the event date.*

An exact rule to determine whether there is none, one or two missing assessments is therefore needed. This rule will be based on the distance between the last adequate tumor assessment date and the event date.

If the distance is larger than threshold D_1 or D_2 then the analysis will assume one or two missing assessments, respectively. The threshold D_1 will be defined as the protocol specified interval between the tumor assessments plus the protocol allowed window around the assessments. Similarly, the threshold D_2 is defined as two times the protocol specified interval between the tumor assessments plus the protocol allowed window around the assessments. In this study, the protocol defined schedule of tumor assessment is every 8 weeks and each assessment is expected to be performed at the scheduled time point plus or minus 1 week, i.e. the window is 2 weeks, then any distance larger than $D_1 = 8+2 = 10$ weeks means one missing assessment and any distance larger than $D_2 = (2*8) + 2 = 18$ weeks means two missing assessments.

The same definition of D_2 will be used to determine the PFS censoring reason.

Possible censoring reasons for PFS are:

- 1: Ongoing without event
- 2: Lost to follow-up
- 3: Withdraw consent
- 4: Adequate assessment no longer available
- 5: Initiation of new cancer therapy
- 6: Event after ≥ 2 missing tumor assessments

PFS censoring reason is then derived by the following sequence of rules.

- If patient is considered to have a PFS event then PFS censoring reason is set to missing.
- Else if patient has had no baseline assessment then PFS censoring reason = 4

- Else if patient has a PFS event after two or more missing assessments (If (PFS Event date <= Censoring date and (PFS Event date - Date of LATA) >= D2)) then CNSRREAS=6:
- Else if patient has no PFS event, and patient is censored at a date after two or more missing assessments ((Censoring date - Date of LATA) >= D2) then CNSRREAS = 4
- Else if censoring date equals the start date of further anti-neoplastic therapy (NWTHYDT) then CNSRREAS = 5
- Else if Censoring date equals date of discontinuation due to consent withdrawal (IFCWDDT) then CNSRREAS = 3
- Else if Censoring date equals date of discontinuation due to loss to follow-up (LOSFUDT) then CNSRREAS = 2
- Else if the Censoring date equal the analysis cut-off date and the time between LATA and the cut-off is greater than D2 days then CNSRREAS = 4
- Else if the Censoring date equal the analysis cut-off date and the time between LATA and the cut-off is less than or equal to D2 days then CNSRREAS = 1

Where min date = minimum of non-missing (analysis cut-off date, start date of further anti-neoplastic therapy, date of withdrawal of consent, date of discontinuation due to loss to follow-up)

Non-measurable disease at baseline

As specified in Section 14 (Appendix II) of the LDK378A2109 protocol, the RECIST 1.1 criteria imply that only patients with measurable disease at baseline should be included in the study. If a patient without measurable disease is enrolled, the intent-to-treat (ITT) principle requires including these patients in the analyses. These patients will be included in analyses based on FAS including patients with either measurable or non-measurable disease and will be excluded from the analyses based on PPS.

As specified in Table 14-8 of Section 14 (Appendix II) of the LDK378A2109 protocol, overall lesion response can be derived for patients without measurable disease at baseline.

Missing baseline tumor assessment

As specified in Table 14-9 of Section 14 (Appendix II) of the LDK378A2109 protocol, since the timing of PD cannot be determined for patients with missing baseline tumor assessment, these patients are censored in the PFS analysis at the date of treatment start. This rule, however, only applies to the 'PD component' of the PFS or DOR assessment.

Patients without baseline tumor assessment who die within D₂ distance from treatment start date will be counted as having an event in the primary analysis of PFS. All deaths will be counted in the OS analysis regardless of presence or absence of the baseline tumor assessment.

Construction of waterfall graphs

The waterfall graphs will be used to depict the anti-tumor activity. These plots will display the best percentage change from baseline in the sum of the diameter of all target lesions for each patient. The proportions of patients with various degrees of tumor shrinkage or growth can then represent a useful efficacy metric.

However, caution needs to be paid to the assessments, where an occurrence of a new lesion or worsening in non-target lesions (resulting in PD as an overall lesion response at given assessment) contradicts the measurements obtained on target lesions. These assessments will not be displayed as bars in the graph. If such a “contradicting” assessment represents the only post-baseline assessment for a patient, then the patient will be represented by a special symbol (e.g. *) in the waterfall graph.

The assessments with unknown target response and also assessments with unknown overall response will be excluded. Patients without any valid assessments will be completely excluded from the graphs.

The total number of patients displayed in the graph needs to be shown and this number will be used as a denominator when calculating the percentages of patients with tumor shrinkage and tumor growth. A footnote will explain the reason for excluding some patients (due to absence of any valid assessment).

All possible assessment scenarios are described in [Table 4-5](#).

Table 4-5 Inclusion/exclusion of assessments used in waterfall graph

Criteria for inclusion/exclusion			Possible source of contradictions	
Target response	Overall lesion response	Include in waterfall	Non-target response	New lesion?
CR/PR/SD	PD	Yes but as * only	PD	any
CR/PR/SD	PD	Yes but as * only	any	Yes
UNK	UNK or PD	No	any	any
CR/PR/SD	UNK	No	UNK	No
CR/PR/SD	CR/PR/SD	Yes as a bar	SD/IR	No
PD	PD	Yes as a bar	any	any

The following algorithm will be used to construct the graph:

1. Select “valid” post-baseline assessments to be included, i.e. for each patient and each assessment repeat the following four steps:
 - 1.1 Check the target lesion response and overall lesion response at each assessment. If at least one of them is UNK then exclude the whole assessment. Otherwise, go to step 1.2.
 - 1.2 Check the overall lesion response. If PD, then go to step 1.3. Otherwise, go to step 1.4
 - 1.3 Check target response. If PD, then go to step 1.4. Otherwise flag the assessment★.
 - 1.4 Calculate the % change from baseline in target lesions.
2. For each patient, go through all valid assessments identified in step 1 and find the assessment with best % change from baseline in target lesions. The “best” means best for the patient, i.e. the largest shrinkage or if a patient only has assessments with tumor

growth take the assessment where the growth is minimal. (*Example 1*: Patient 1 has the following % changes from baseline at assessments 1, 2, 3, 4 and 5, respectively: -10%; -25%; -13%; -4% and +6%. His/her best % change is then -25%. *Example 2*: Patient 2 has the following % changes from baseline at assessments 1, 2 and 3, respectively: +5%; +18% and +35%. His/her best % change is then +5%).

3. Construct the waterfall graph displaying the best % change from baseline for each patient. Patients having only ★ flagged assessment(s) will be displayed separately.

Both BIRC assessment and investigator assessment will be used in the construction of the waterfall plot.

The recommended way of the display from left to right is:

1. Bars under the horizontal axis representing tumor shrinkage
2. Bars above the horizontal axis representing tumor growth
3. “Zero” bars with ★ symbol representing patients with contradiction
4. ‘#’ below or above the vertical bars represent patients with a PFS event.

4.2.2 Sources for overall lesion response

The tumor endpoints derivation is based on the sequence of overall lesion responses at each assessment/time point. However, the overall lesion response at a given assessment/time point will be provided from different sources as illustrated in [Table 4-6](#).

Table 4-6 Sources for overall lesion response

Source 1	Investigator (local radiology) reported overall lesion response
Source 2	BIRC (Blinded Independent review committee) reported overall lesion Response

In this study, Source 1 will be used for the key secondary endpoint (ORR) derivation and other secondary endpoint calculations per investigator (DOR, DCR, TTR, OIRR and PFS).

For secondary endpoints based on BIRC assessment (ORR and OIRR), Source 2 will be used for the endpoint derivation.

4.2.3 Kaplan-Meier estimates

To analyze time to event variables (PFS, OS, DOR and TTR), an estimate of the survival function will be constructed using Kaplan-Meier (product-limit) method as implemented in PROC LIFETEST with METHOD=KM option (see example below). The median time to event and estimated event rates at different time points will be estimated, along with associated 95% two-sided CIs derived based on the complementary log-log transformation. This will be conducted via the SAS procedure LIFETEST. The TIME statement will include a variable with survival times (survtime in the example below) and a (right) censoring variable (censor in the example below) with a value of 1, representing censoring:

```
PROC LIFETEST data = dataset
```

```
  METHOD = KM
```

```
  CONFTYPE=LOGLOG;
```

CONFIDENTIAL - For Business Use Only

```
TIME survtime*censor(1);
```

```
RUN;
```

```
/* survtime represents variable containing event/censor times;  
censor represents censoring variable (1 = censored, 0 = event); */
```

Kaplan-Meier survival and failure function estimates from this procedure will be used to construct the Kaplan-Meier figures.

Median survival will be obtained along with 2-sided 95% CIs calculated from PROC LIFETEST output using the method of [Brookmeyer & Crowley, 1982](#).

Kaplan-Meier estimates with 2-sided 95% CIs at specific time points will be summarized. The time points can be expressed in weeks or in months depending on the time-to-event variable. The CIs will be constructed using Greenwood's formula [[Collett, 1994](#)] for the standard error of the Kaplan-Meier estimate.

The Kaplan-Meier curves, medians and Kaplan-Meier estimates with 95% CIs at specific time points will also be displayed.

The PROC LIFETEST statement will use the option CONFTYPE=LOGLOG. The CONFTYPE option specifies the transformation applied to the survival function to obtain the point-wise confidence intervals and the confidence intervals for the quartiles of the survival times. The LOGLOG keyword specifies the complementary log-log transformation ([Collett, 1994](#)) $g(x) = \log(-\log(x))$ which ensures that the point-wise confidence intervals are always within interval $[0, 1]$. Although the LOGLOG is the default option in SAS v 9.1, it should be explicitly shown.

The Kaplan-Meier graphs will be constructed using SAS software.

4.2.4 OIRR calculations in patients with measurable brain metastases

A patient with measurable brain metastases at baseline is defined as a patient having at least 1 target lesion in brain. Inclusion of response assessments based on lesion locations in the brain for each assessment (including baseline to identify whether patients have measurable brain metastases) uses the following list of terms collected based on investigator and BIRC tumor data: brain lesions, brain (multiple, right frontal, left temporal left parietal), brain metastases (occipital, multiple, bilateral diffuse, bilateral cerebral, cerebellum), CNS, cerebellum, cerebral cortex (frontal, occipital, parietal or temporal). The following steps will be taken to calculate the best overall intracranial response (BOIR) for patients with measurable brain metastases at baseline:

1. If only target lesions in brain and no non-target lesions in brain are identified at baseline, calculate the longest diameter from all lesions in the brain (selected from list above), and new lesions in brain (if any, based on the list) to derive responses per assessment. Non-target lesion response status is not considered since no non-target lesions were identified in the brain at baseline.
2. If both target and non-target lesions in the brain are identified at baseline, calculate the longest diameter from all lesions in the brain (selected from list above), use all non-target

lesions response status in the brain (selected from list above) and new lesions in the brain (if any, based on the list) to derive responses per assessment.

3. For each assessment, derive overall intracranial response.
4. For the whole set of derived overall intracranial responses, calculate BOIR.

For this subset of patients, calculate OIRR.

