14.2.2.3 Baseline documentation of target and non-target lesions

For the evaluation of lesions at baseline and throughout the study, the lesions are classified at baseline as either target or non-target lesions:

- **Target lesions:** All measurable lesions (nodal and non-nodal) up to a maximum of five lesions in total (and a maximum of two lesions per organ), representative of all involved organs should be identified as target lesions and recorded and measured at baseline. Target lesions should be selected on the basis of their size (lesions with the longest diameter) and their suitability for accurate repeated measurements (either by imaging techniques or clinically). Each target lesion must be uniquely and sequentially numbered on the CRF (even if it resides in the same organ).

Minimum target lesion size at baseline

- **Non-nodal target:** Non-nodal target lesions identified by methods for which slice thickness is not applicable (e.g. clinical examination, photography) should be at least 10 mm in longest diameter. See [Section 14.2.2.1.1](#).
- **Nodal target:** See [Section 14.2.2.1.1](#).

A sum of diameters (long axis for non-nodal lesions, short axis for nodal) for all target lesions will be calculated and reported as the baseline sum of diameters (SOD). The baseline sum of diameters will be used as reference by which to characterize the objective tumor response. Each target lesion identified at baseline must be followed at each subsequent evaluation and documented on eCRF.

- **Non-target lesions:** All other lesions are considered non-target lesions, i.e. lesions not fulfilling the criteria for target lesions at baseline. Presence or absence or worsening of non-target lesions should be assessed throughout the study; measurements of these lesions are not required. Multiple non-target lesions involved in the same organ can be assessed as a group and recorded as a single item (i.e. multiple liver metastases). Each non-target lesion identified at baseline must be followed at each subsequent evaluation and documented on eCRF.

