14.2.2.5 Evaluation of overall lesion response

The evaluation of overall lesion response at each assessment is a composite of the target lesion response, non-target lesion response and presence of new lesions as shown below in Table 14-7.

Table 14-7 Overall lesion response at each assessment

Target lesions	Non-target lesions	New Lesions	Overall lesion response
CR	CR	No	CR ¹
CR	Non-CR/Non-PD ³	No	PR
CR, PR, SD	UNK	No	UNK
PR	Non-PD and not UNK	No	PR1
SD	Non-PD and not UNK	No	SD ^{1, 2}
UNK	Non-PD or UNK	No	UNK ¹
PD	Any	Yes or No	PD
Any	PD	Yes or No	PD
Any	Any	Yes	PD

¹ This overall lesion response also applies when there are no non-target lesions identified at baseline.

² Once confirmed PR was achieved, all these assessments are considered PR.

³ As defined in [Section 14.2.2.4](#)

If there are no baseline scans available at all, then the overall lesion response at each assessment should be considered Unknown (UNK).

If the evaluation of any of the target or non-target lesions identified at baseline could not be made during follow-up, the overall status must be ‘unknown’ unless progression was seen.

In some circumstances it may be difficult to distinguish residual disease from normal tissue. When the evaluation of complete response depends on this determination, it is recommended that the residual lesion be investigated (fine needle aspirate/biopsy) to confirm the CR.

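### The SAP's derivation of intracranial response (OIRR) names the longest brain diameter where RECIST needs a sum, and a second SAP section sources OIRR from the all-site response; read literally, either can misclassify patients

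*SAP*

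**What the plan says.** Protocol 10.5.2.1 defines OIRR as an ORR restricted to target and non-target lesions in the brain, counting confirmed CR or PR per RECIST 1.1. Protocol Appendix 2 sets the size measure. Section 14.2.2.3 forms a sum over all target lesions (long axis for non-nodal lesions) and adds: "The baseline sum of diameters will be used as reference by which to characterize the objective tumor response". Table 14-5 then defines PR as a fall of at least 30% in that sum from baseline, and PD as a rise of at least 20% and at least 5 mm from the smallest sum. At most two target lesions are allowed per organ.

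SAP 3.2.10.2 refers the reader to SAP 4.2.4 for the OIRR calculation. Step 1 of 4.2.4 (brain targets only) and step 2 (brain targets and non-targets) both instruct the programmer to "calculate the longest diameter from all lesions in the brain (selected from list above"). The word sum does not appear in that section. Step 3 continues: "For each assessment, derive overall intracranial response".

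SAP 4.2.2 covers the source of responses. Source 1 is the "Investigator (local radiology) reported overall lesion response", and it is assigned to ORR and to "other secondary endpoint calculations per investigator (DOR, DCR, TTR, OIRR and PFS"). For the central review the section says: "For secondary endpoints based on BIRC assessment (ORR and OIRR), Source 2 will be used for the endpoint derivation". Protocol 14.2.2.5 explains what an overall lesion response is: "The evaluation of overall lesion response at each assessment is a composite of the target lesion response, non-target lesion response and presence of new lesions". Nothing in that definition restricts it to one organ.

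**The concern.** There are two separate problems.

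**Size measure.** The longest diameter among several lesions and the sum of their diameters are different quantities, and the RECIST cut-offs of -30% and +20% are defined on the sum. SAP 4.2.4 is the section a programmer would code from.

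**Source.** SAP 4.2.2 and SAP 4.2.4 cannot both be followed. The first takes a response already reported across all sites; the second builds a new response at each visit from brain lesions alone. A patient can be a responder under one and a non-responder under the other.

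OIRR is a named secondary endpoint by both investigator and BIRC. SAP 4.1.1 records no difference between SAP and protocol, so neither departure has been declared as intended.

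**Working it through.** The plan gives no OIRR figure to reproduce. The check applies the protocol's own rule to example lesions.

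**The RECIST rule, on the protocol's worked example (14.2.3.1).** Baseline sum 200 mm, then 140, 150, 140, 160, 160 mm. Changes from baseline: -30%, -25%, -30%, -20%, -20%. The second 140 mm confirms the PR, and 160/140 - 1 = +14.3% is short of PD. The sequence is PR, SD, PR, PR, PR, as the protocol states.

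**Sum against single longest diameter, at one assessment against baseline.** Lesion sizes are assumed; thresholds are from Table 14-5.

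| Brain targets, mm | Change in sum | Class | Change in longest | Class |
|---|---|---|---|---|
| 20+10 to 12+12 | 24/30 - 1 = -20% | SD | 12/20 - 1 = -40% | PR |
| 26+14 to 20+5 | 25/40 - 1 = -37.5% | PR | 20/26 - 1 = -23% | SD |
| 20+10 to 20+17 | 37/30 - 1 = +23.3%, +7 mm | PD | 20/20 - 1 = 0% | SD |
| 30 to 20 (one target) | 20/30 - 1 = -33.3% | PR | -33.3% | PR |

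The error runs in both directions and needs two brain targets. With one target the two measures coincide.

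**All-site against brain-only response.** Take the second row, a brain PR in which the brain sum falls by 15 mm from 40 mm. Suppose the extracranial targets total E mm at baseline and do not change. The all-site change is -15/(40 + E). It is smaller than 30% once 40 + E exceeds 15/0.30 = 50, that is, once E exceeds 10 mm. Ten millimetres is the smallest measurable non-nodal lesion in Appendix 2, so almost any unchanged extracranial target turns this brain PR into an all-site SD.

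The reverse also occurs. In the first row the brain is SD, with a fall of 6 mm from 30 mm. The all-site response becomes PR when the extracranial fall reaches 0.30 × (30 + E) - 6 = 3 mm + 0.30 × E, provided non-target lesions have not progressed and no new lesion appears.

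**How often the size measure matters.** The documents give no brain lesion sizes, no count of patients with two brain targets and no OIRR denominator. An illustrative simulation of two-target patients used baseline diameters uniform on 10-30 mm, log-ratio SD 0.3-0.5 and between-lesion correlation 0.3-0.8. PR status differed in about 7-13% when the median ratio was 0.7, and in about 1-8% when it was 0.4. A median ratio of 0.7 lies exactly on the PR threshold, where disagreement is easiest. The simulation uses a single assessment, whereas OIRR needs a confirmed response. These percentages show only that the answer depends on the assumptions.

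**The case against.** The strongest defence is that this is loose drafting inside a plan that otherwise points the right way. SAP 4.2 says response is evaluated under the protocol's RECIST 1.1 appendix, and SAP 3.2.10.2 describes OIRR as a brain response per RECIST 1.1. The longest diameter of each lesion is what one adds up for non-nodal lesions, so the phrase may be shorthand for collecting them. No passage sets a response threshold for a single longest diameter. SAP 4.2.2 may be meant only to say whose reading is used, investigator or BIRC.

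Much of that stands, and it defeats several stronger readings that a reader might infer:

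- **That OIRR will not be the protocol's RECIST brain response.** The deferral to Appendix 2 means a careful programmer could still produce it.
- **That the measurement takes in non-target lesions.** Step 1 applies only when the brain has no non-targets at baseline. Step 2 brings non-targets in by status, and protocol 14.2.2.3 does not require them to be measured.
- **That assessments after new anticancer therapy are admitted.** Step 4 reads "For the whole set of derived overall intracranial responses, calculate BOIR", which could suggest no cut-off. But the protocol defines OIRR as an ORR, and the best-response rules in SAP 3.2.10.1 and protocol 14.2.3.1 already exclude such assessments. The step does not waive them.
- **That the size of the error in OIRR is known.** It is not, for the reasons given in the working.

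The defence does not reach two things. SAP 4.2 says the text beneath it supplies the detailed programming rules, so its general deferral does not cancel a specific instruction. Nor does it reconcile 4.2.2 with 4.2.4: Sources 1 and 2 are defined as reported overall lesion responses, not as a choice of reader for lesion-level data.

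**Conclusion.** The point holds as an ambiguous and internally inconsistent derivation that should be corrected. SAP 4.2.4 does not state the RECIST sum of brain target diameters, and SAP 4.2.2 names a source that cannot yield an intracranial response. Coded literally, the first can move patients with two brain targets across the PR or PD threshold in either direction, and the second replaces brain response with whole-body response.

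The conclusion rests on comparing the texts and on arithmetic with assumed lesion sizes. It assumes nothing about which version was actually programmed, and no effect on the reported OIRR can be quantified. The consequence is confined to one descriptive secondary endpoint in patients with brain disease at baseline. The primary PK and safety objectives and the key secondary ORR are unaffected.

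**What to change.** In SAP 4.2.4, steps 1 and 2, replace the longest-diameter phrase with: *calculate the sum of diameters of the brain target lesions at baseline and at each assessment*. Add that Tables 14-5 to 14-7 of the protocol apply to brain target lesions, brain non-target lesions and new brain lesions only.

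In SAP 4.2.2, remove OIRR from the Source 1 and Source 2 lists. State that it is derived under 4.2.4 from lesion-level brain data, as recorded by the investigator or by BIRC respectively.

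The cost is two wording changes and a check of the OIRR program against them. No new data are needed.
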